A particularly challenging morbidity in this patient population is the development of persistent, chronic pain. Interestingly, as many as 28% of survivors continue to have moderate pain six months after treatment completion (2). Not only is this distressing for the patient, but the continued use of opioids months or years after curative treatment further contributes to the burden of the ongoing national opioid epidemic (3). Opioid use is associated with its own deleterious side effects which include difficult access to medication, risk of overdose, addiction, gastrointestinal dysmotility, and obtundation. In addition, these chronic pain states are closely associated with the development of depression, anxiety, cognitive dysfunction, and sleep disturbances which are further detrimental to quality of life (4, 5).

Head and neck (H&N) cancer patients often undergo rigorous treatments which involve chemotherapy, radiation, and surgery. As a result, these patients are highly susceptible to the development of acute and chronic pain. Initially, pain in this population can manifest as acute, well-localized nociceptive pain or neuropathic pain from direct nerve injury. In most cases, these types of pain can be treated with NSAIDs, acetaminophen, and/or opioids during treatment. However, some patients will gradually develop an increasing sensitivity to pain that extends beyond the course of treatment. In extreme cases, patients experience exaggerated pain responses to noxious stimuli (hyperalgesia), painful responses to innocuous stimuli (allodynia), pain in areas unaffected by cancer or its related treatments, and other systemic symptoms of neurological impairment such as fatigue, cognitive dysfunction, and mood disturbances. In this particular subset of patients, the pathogenesis of this exaggerated pain phenotype is highly reminiscent of an amplified pain state also known as central sensitization. In the presence of a repetitive noxious stimulus, the threshold for pain in nociceptive receptors is lowered as a protective mechanism (primary hyperalgesia) (6). The exaggerated response to pain eventually returns to baseline after removal of the stimulus. However, in chronic pain states, overamplification of the nociceptive pathway and dysfunction of inhibitory pathways in the central nervous system leads to permanent pathological pain amplification, known as central sensitization. This manifests clinically as secondary hyperalgesia (pain outside of the site of injury), allodynia, and/or widespread pain (7).

The literature regarding pain in cancer survivors is still in its infancy given the increasing number of curative therapies leading to longer rates of survival after treatment. What we are just now starting to realize is that specific pain phenotypes are unique to specific types of cancers and consequently require different types of pain regimens. However, lack of education and consensus definitions in the classification of pain have resulted in continued opioid use long after commencement of cancer treatment, leading to increased tolerance and escalating doses in the cancer survivor population. Perhaps the most well documented cancer pain syndrome is post-mastectomy pain syndrome (PMPS). The incidence of pain after breast surgery has been reported to

be around 20-50% (8-11). This variability can be attributed to the lack of a consensus definition to describe PMPS (12). In addition, different types of pain are encompassed within the single definition of PMPS. Patients may suffer from pain overlying scar tissue, direct nerve injury, phantom breast pain, pain from impaired lymphatic drainage, and/or musculoskeletal pain just to name a few (13). To complicate matters further, each of these pain phenotypes have differing underlying mechanisms which include pain induced by local inflammation and destruction sensed by nociceptors, neuropathic pain due direct injury to the peripheral and central somatosensory system, central sensitization from abnormal ascending and descending pain processing mechanisms, or mixed pain (14, 15). As one can image, the underlying pathogenesis of pain strongly determines the response to specific medications and account for treatment failure. In fact, trials that examine treatment effect in a population of patients without proper pain classifications may lead to negative results (16). Thus, cancer type specific classifications of pain and their underlying pathogenesis must be carefully studied in order to establish effective clinical trials for the prevention and treatment of pain in cancer survivors.

Classically, central sensitization is a feature of several chronic pain states such as fibromyalgia, irritable bowel syndrome, and temporomandibular disorder (17). Although these conditions are seemingly heterogeneous in nature with varying anatomical focal points of amplified pain, the syndromes themselves encompass many of the same systemic symptoms as described above. These central sensitivity syndromes are often difficult to treat because an identifiable cause or trigger remains to be elucidated. It has been speculated that genetic predisposition, neuro-inflammation involving both the innate and adaptive immune systems, and rewiring of the pain circuitry in the central nervous system are all involved (17-20). However, the natural progression of these disease states is difficult to follow because patients often present after the disease process is already well underway.

Recently, imaging modalities have garnered much interest in identifying structural and functional changes in the brains of patients with central sensitivity states. In fibromyalgia patients, there is both decreased and increased grey matter volume and increased connectivity in brain areas responsible for the anticipation of, attention to, and emotional processing of pain (21-23). Resting state functional magnetic resonance imaging (fMRI) scans measure basal metabolic signatures during periods of "rest" that can reveal underlying connectivity of different areas of the brain and have been shown to be amplified in patients with central sensitization syndromes such as fibromyalgia, chronic fatigue, irritable bowel syndrome, temporomandibular joint disorder patients (24). Structural alterations such as grey matter volume can also be measured using structural MRI measurements in areas of the brain that are associated with stress, pain, emotional processing, and memory development. A combination approach of quantitative sensory testing (25) along with fMRI imaging has been used to correlate pain thresholds with brain activity in the fibromyalgia patients (23). In these studies, a stimulus of increasing intensity (vibratory, thermal, or pressure) is administered in a step-wise fashion and changes in blood flow (and therefore activity) to specific brain regions are assessed. These types of studies have shown that lower pain thresholds correlate well with earlier activation of pain centers in patients with fibromyalgia when compared to negative controls. Although these studies have made great strides in unveiling the dynamic processes involved in central sensitization, the sequential events leading to the development of the central sensitivity syndromes are still unknown. This is because the existing literature only provides a snapshot of ongoing pathological pain processes since these patients present only after

disease onset. This is supported by the conflicting structural and functional MRI data in the literature which is likely due to a heterogeneous patient population who may be in distinct stages of disease progression.

Upon initial diagnosis, most H&N cancer patients present with localized nociceptive pain but the combination of surgical resection and radiation therapy commonly causes acute and chronic pain localized to the involved area of the head and neck region. What is less well recognized is that 23% of H&N cancer survivors report persistent moderate to severe widespread pain that may last indefinitely (21, 26). In addition, H&N cancer patients often present with other systemic symptoms such as depression, anxiety, and cognitive dysfunction that can severely affect their quality of life. Given the relatively high occurrence of what resembles a central sensitivity state in this patient population and the potentially trackable development of this state during the course of cancer treatment, the H&N cancer population provides an exceptional model system for studying the pathogenesis of central sensitization in real-time.

We hypothesize that central sensitization is a key pathological process that occurs in a subset of H&N cancer patients who experience chronic pain beyond treatment completion. In our pilot study, we propose to conduct a cross-sectional study of H&N cancer survivors who have completed multimodal treatment to assess and characterize the presence of distinct pain phenotypes: localized, nociceptive pain versus centralized pain. Using structural and functional MRI, we will determine if a distinct brain signature similar to other central sensitivity syndromes is present and if we can distinguish central from non-central (normal, nociceptive) pain in this specific population. We will also document the presence of other systemic symptoms such as fatigue, mood disturbances, neurocognitive changes, and sleep disturbances to see if the culmination of specific symptoms correlates to the presence of distinct MRI signals to predict and diagnose central sensitization in these patients. This study will aim to answer several important questions. 1) Does central sensitization play a role in the pathogenesis of chronic pain in H&N cancer survivors? 2) Can we objectively and reliably measure nociceptive versus centralized pain in this population? 3) Does this objective brain signature correlate to the presence of specific subjective symptoms?

The answers to these questions will provide us with the foundation for future studies in which we hope to characterize the evolution and progression of central sensitization in this unique patient population. This will allow us to eventually guide personalized treatment regimens for treating and preventing central pain in the cancer population using multimodal, non-opioid based regimens. It will also provide us with a rare opportunity to expand our knowledge in the pathogenesis of central sensitization that will be globally applicable to other centralized pain syndromes.

2.0 Study Summary and Specific Aims:

Summary: We propose to conduct a cross-sectional pilot study of H&N cancer survivors who have completed multimodal treatment to assess and characterize the presence of distinct pain syndromes. We plan to screen patients who have completed head and neck cancer therapy using a battery of patient reported outcome measures (PRO's). Based on the PRO responses, patients will be characterized as follows: 1) no pain, 2) central pain, and 3) nociceptive pain. Patients will then undergo structural and functional magnetic resonance imaging

(MRI). We will correlate clinical presentation with MRI signatures to determine if distinct signatures can be identified for each cohort. In addition, we propose to correlate the clinical and MRI signatures for central pain with the presence of other systemic symptoms. Participants will be asked to fill out several questionnaires that capture systemic symptoms commonly associated with other central sensitivity syndromes.

Aim 1: To correlate structural and functional MRI signature with one of three pain phenotypes in H&N cancer survivors: 1) no pain, 2) central pain, and 3) nociceptive pain.

Hypothesis 1: Structural and functional MRI can identify unique signatures that correspond with pain phenotype.

Aim 2: To correlate the presence of chronic systemic symptoms with pain phenotype.

Hypothesis 2: Patients with central pain will have an increased frequency of other systemic symptoms (fatigue, neurocognitive dysfunction, depression, etc.) as measures on the General Symptom Survey.

Exploratory Aim: DNA, RNA, and plasma will be collected for genomic, transcriptomic, and proteomic studies. Results will be vertically integrated along with the results of clinical studies described within this protocol to identify targets for future correlative studies.

3.0 Methods:

Patient Eligibility:

Inclusion Criteria:

- Patients with histologically proven head and neck cancer
- Patients without a diagnosis of head and neck cancer (up to 10 patients, see below)
- Completed multi-modality therapy a minimum of 6 weeks prior to study entry.
- Willing and able to provide informed consent
- All participants must be at least 21 years of age
- Able to speak English

We anticipate enrolling a total of 75 patients with a history of head and neck cancer who will complete all questionnaires and MRI scanning. We will also recruit up to 10 patients WITHOUT a diagnosis of head and neck cancer to facilitate optimization of the MRI scanning processes. This will allow us to address logistical issues, such as pressure stimulator setup and timing of each scan to be performed.

Exclusion Criteria:

- Patients who are pregnant. See below under “Study Procedures” section on pregnancy testing.
- Patients who are unable to lie still.
- Patients who are unable tolerate pressure stimulator.
- Non-MRI compatible devices such as aneurysm clips, cardiac pacemakers or defibrillators, cochlear implants, hardware, or any other implants
- Iron-based tattoos, pieces of metal (bullet, BB, shrapnel) close to or in an important organ (such as the eye), or other non-MRI compatible metal in the body.

Study Procedures:

Recruitment

The attending physicians, nurse practitioner or nurses in the Oncology Clinic routinely review the list of patients presenting to clinic for follow-up visits. All patients who are a minimum of 6 weeks post treatment will be provided with information about the study and asked if they are interested in study participation. If patients express interest, trained study staff will be notified. Study staff will meet with all interested patients to discuss the study in more detail and answer questions.

Informed Consent Process

Research staff will obtain informed consent from the study participants before initiation of data collection. This process will take place in a quiet, private location at Vanderbilt Medical Center to ensure confidentiality. During the informed consent process, a copy of the IRB-approved consent form will be provided to prospective study participants. Research staff will review the study risks, potential benefits, and procedures to assess confidentiality and data de-identification. Prospective study participants will be assured that their participation in the study is voluntary, and that they can withdraw at any point in the study by notifying research staff. Participants will be provided with research staff contact information. Prospective study participants will be informed that refusal to participate in the study or withdrawal from the study will not affect their care. After verbally reviewing the informed consent documents, prospective participants will be allotted ample time to read the consent form or have the consent form read to them aloud. Research staff will verify comprehension of the informed consent process, and then ask the prospective participant if they wish to enroll on the study. If so, prospective study participants will be instructed to sign the IRB-approved consent form. In addition, research staff obtaining informed consent will sign the form. The study participant will then be provided with a copy of the signed consent form. The research staff will have received training in obtaining informed consent.

The original signed IRB-approved consent form will be stored in a locked file drawer in the study office or stored in the password protected REDCap database if applicable. The informed consent document will be scanned into the study participant's electronic medical record. Alternatively, we will use an electronic consent form that will be completed on the REDCap database.

Pressure Stimulator Testing

At the time of enrollment and after the informed consent has been signed, the study staff can demonstrate the use of the pressure stimulator (IPC-1000 (27)) in the clinic if requested by the patient. These systems are computer-controlled, MRI-compatible pressure stimulators that allow for remote delivery of a stimulus that can be used in synchronization with imaging sequences if needed. Patient pain responses can be recorded in real time to varying degrees of pressure inside or outside the MRI machine. The pressure stimulus is delivered to the thumbnail via a thumbnail pressure stimulator. Those who are unable to tolerate the pressure stimulator will not proceed with the study.

On the day of the MRI scans, we will conduct two separate tests. First, we will measure the pain threshold (when pain is >0) and tolerance (when pain is unbearable) to a pressure stimulus as previously described in the literature (28). This information will be used to calculate an individualized pressure intensity for the next test (29, 30). Next, we will test for central sensitization using the slowly repeated evoked pain protocol. This

test consists of delivering a five-second pressure stimulus with a 30 second rest period repeated for a total of 9 times. The sequence of events is anticipated to be as follows:

Pain Threshold and Tolerance Testing

1. Delivery of 0.5 kgf/cm² pressure stimulus to dominant thumbnail for 5-10 seconds using the automated system.
2. Patient rates pain intensity of stimulus from a scale of 0-100.
3. 20 second rest period (patient will not be told how long to prevent anticipation).
4. Repeat steps 1-3 with increasing levels of pressure in 0.5 kgf/cm² increments until participant asks to stop, pain intensity is >80/100, or maximum pressure of 10 kgf/cm².

5-10 minute rest period

Slowly Repeated Evoked Pain Testing

1. The intensity of the stimulus will be determined by using the following equation:
Individualized SREP intensity = Threshold + 1.25*(DF/4), where DF = Tolerance-Threshold (ref)
2. Delivery of individualized SREP intensity pressure stimulus to non-dominant thumbnail for 5 seconds using automated system.
3. After 5 seconds, patient rates pain intensity of stimulus from a scale of 0-100.
4. 20-30 second rest period (patient will not be told how long to prevent anticipation).
5. Repeat steps 2-4 eight more times.

The average time to test completion is less than 12 min based on the literature. We believe that most patients will be able to tolerate this stimulus. In a recent study by Harte *et. al.* (28), tolerability of the pressure stimulus was high and only 10 out of 298 patients opted out. They were able to obtain data for 62 patients with urologic chronic pelvic pain syndrome at the initial visit and 52 measurements at a 6 month follow-up visit. In fact, the pressure pain stimulus protocol has been adapted from this article. However, those who are unable to tolerate the stimulus will not be included in the anticipated accrual goal count.

Since the initiation of study, we have recruited and tested 3 subjects. For those who have already completed the study, we will attempt to repeat the pain threshold and tolerance testing along with the slowly repeated evoked pain testing during a future clinic appointment. All other enrolled subjects who have not completed the study will undergo the entirety of the protocol on the day of MRI scanning.

Exclusion of Pregnant Women

Although MRI has not shown to affect pregnancy, those who are pregnant will be excluded from the study. Women of reproductive age will be asked to take a pregnancy test after informed consent has been obtained. The pregnancy test will be conducted on the day of the MRI scan. Those who have had bilateral oophorectomies, hysterectomy, and/or tubal ligations will be excluded from pregnancy testing. If pregnancy test is declined, the patient will be excluded from the study.

PRO Data Collection

Disease and treatment data (e.g. type and stage of cancer, date of cancer diagnosis) will be obtained from the participant's medical record review by study staff at Vanderbilt.

After patients have signed informed consent, they will be scheduled for study related activities at a time that is convenient to them. All patients will complete the Sociodemographic Data Collection Form, the Vanderbilt Head and Neck Symptom Survey plus General Symptom Survey Version 2.0, Profile of Mood States-Short Form, Neurotoxicity Rating Scale, the Quality of Life Assessment, Central Sensitivity Inventory, the Fibromyalgia Diagnostic Tool, and the Head and Neck Pain Inventory.

Blood Draw:

About 20% of the H&N cancer population develop long-term pain and systemic symptoms after treatment. However, the risk factors associated with the presumable development of central sensitization in this specific patient population have not been identified. To better understand the molecular basis of this treatment complications, patients will undergo phlebotomy for future molecular analyses. DNA, RNA, and plasma will be collected for genomic, transcriptomic, and proteomic studies. Results will be vertically integrated along with the results of clinical studies described within this protocol to identify targets for future correlative studies.

At the time of MRI, blood will be drawn from each patient. Up to 20 ml of blood will be divided for RNA, DNA, and plasma extraction. A portion of the blood will be divided into PAXgene tubes for RNA extraction. The remainder of the blood will be separated into plasma for proteomic analysis and cells for DNA extraction. Samples will be stored at -80C until ready for processing.

Phenotype Designation:

Following completion of the questionnaires, the patient's responses will be reviewed by the principle investigator. Patients will complete the Central Sensitivity Inventory questionnaire, the Fibromyalgia Diagnostic Tool, and the Head and Neck Pain Inventory to determine inclusion into each cohort. Using criteria established in the non-oncologic patient population, patients will be assigned to one of three cohorts by three independent reviewers ([name], [name], and [name]): those with 1) no pain, 2) central pain and 3) nociceptive pain. At least two out of three reviewers must agree with each assignment. 25 patients from each of the principle cohorts will proceed to structural and functional MRI testing. Recruitment will continue until all three cohorts are filled. The patient's participation will be concluded.

Structural and Functional MRI Testing:

The study staff will schedule MRI testing at a time that is convenient for the patient. The procedure will take approximately 1.5-2 hours.

Compensation:

Upon completion of the MRI, patients will be provided with a \$50.00 gift card to compensate them for their time and effort.

4.0 Measures:

Questionnaires:

Demographic Data Form: Patients will be asked to report their birthdate, gender, race, ethnic category, highest educational level, marital status, employment status, area of residence, insurance coverage, and annual household income.

Vanderbilt Head and Neck Symptom Survey plus General Symptom Survey version 2.0 (VHNSS v2.0 plus GSS): The VHNSS v2.0 (31) assesses the prevalence and severity of treatment-related symptoms and their functional impact in patients with head and neck cancer. The VHNSS v.2.0 consists of 50-items within 13 domains including nutrition, swallowing, xerostomia, mucositis, excess mucus, speech, hearing, taste change, smell, dental health, mucosal sensitivity, range of motion, and pain. Items are scored on a numeric scale rating the severity of the symptom from 0 (none) to 10 (severe). The VHNSS v.2.0 takes approximately 10 minutes to complete. VHNSS v2.0 plus GSS includes 12 additional items directed at the systemic effects of therapy.

Profile of Mood States-Short Form (POMS-SF): The POMS-SF is a 37-item scale is composed of six subscales: depression, vigor, confusion, tension, anger and fatigue. Cronbach's alphas ranged from 0.78 to 0.91. It correlates well with other measures of mood and physical function, yet it has the benefit of a short administration time.

Neurotoxicity Rating Scale (NRS): The NRS is a 37 item instrument whose items reflect symptoms associated with neurotoxicity of medical treatment (32). Participants rate the severity of all of the 37 item, 5 point Likert-like scale that rates neuropsychiatric symptoms on a scale of "not present" to "extremely severe."

Quality of Life: QOL will be measured using Cantril's Ladder, a single item self-anchoring scale (33, 34). The measure asks patients to rate their current quality of life on a scale ranging from 0 to 10, with higher scores indicating better overall quality of life. Discriminant validity has been supported by significantly lower scores in patients with rheumatoid arthritis than in healthy controls (35). Construct validity has been supported by a positive relationship between scores on to social role retention in survivors of bone marrow transplantation (36). A 5 item domain-specific QOL questionnaire will also be used.

Central Sensitivity Inventory (CSI): The CSI is a two-part survey consisting of 35 questions (37). Part A asks patients to identify systemic symptoms as being present "never", "rarely", "sometimes", "often", or "always". Part B determines whether patients have been previously diagnosed with central sensitivity syndromes or other related disorders. Only Part A is used for scoring.

Fibromyalgia Diagnostic Tool (FDT): The FDT is a questionnaire developed based on the revised American College of Rheumatology's diagnostic criteria for fibromyalgia from 2016 (38). It combines the widespread pain index and the symptom severity scale to aid in the diagnosis of fibromyalgia and the severity of the disease. We will adapt the use of this diagnostic tool for the H&N cancer patient population to detect the presence of a central sensitivity phenotype.

Head and Neck Pain Inventory (HNPI): The HNPI is a diagram in which patients can document specific areas of pain with an emphasis on the head and neck region. The patients are also asked to rate their pain on a scale

of 1-10 in the past week, describe the type of pain they are experiencing, and document any treatments for their pain.

Opioid Risk Took (ORT): The ORT is a self-reporting screening tool for adults to assess the risk for potential opioid abuse in patients with chronic pain. A score of <3 indicates low risk, 4-7 moderate risk, and >8 high risk (39).

MRI protocol:

Standardized protocols developed by investigators in the Imaging Center will be used for the structural and fMRI sessions. The scans will be acquired in order of importance. The study PI and/or appropriately trained key study personnel will be present at the time of imaging. The anticipated time to complete all of the following is estimated to be about 60 to 90 minutes. Physiologic data, such as heart rate and respiratory rate, will be collected using a pulse-oximeter on the non-dominant hand and a chest plethysmograph around the subject's abdomen. These physiologic parameters have been shown to influence fMRI data acquisition and analysis. The following MRI scans will be acquired:

- **Baseline structural and resting state fMRI:**
Patients will be placed in scanner and acquisition of structural and resting state fMRI will be performed. Imaging will occur for a period of about 10-20 minutes while the patient is “resting” but not asleep.
- **fMRI in the presence of noxious stimulus:**
The pressure stimulus will be delivered via the IPC-1000 as described above. These systems are computer-controlled and MRI-compatible so that a pressure stimulus can be administered in synchronization with imaging sequences. They allow for participant feedback during image collection so that patient pain responses can be recorded in real time. A pressure stimulus of XX will be delivered in a block design to the dominant thumbnail using the IPC-1000 for 5-30 second intervals with 5-30 second intervals of rest at an intensity that produces a pain score of 50 (characterized as “moderate pain”) as determined by previous testing in the clinic OR a pre-specified intensity of 2-4 kg/m². This range produces an average pain score of 4-5/10, considered a “moderate” intensity, in fibromyalgia patients and has been used frequently in the literature (27, 40, 41). The scan is expected to take no longer than 10-20 minutes.
- **Diffusion Tensor Imaging:**
Following the completion of the stimulus scans, patients will undergo Diffusion Tensor Imaging in the resting state. This will take on average about 10-20 minutes.

Blood Draws:

Blood will be drawn before or after the above studies by staff trained in phlebotomy. Blood will be appropriately labeled, processed, and stored in a -80 degree freezer.

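### Survivors may enter at any time from 6 weeks after treatment, and time since treatment is not used in the cohort comparison, so it can confound that comparison by an unknown amount in either direction

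*Combined protocol and SAP*

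**What the plan says.** **Entry.** Under Inclusion Criteria in section 3.0, a survivor must have "Completed multi-modality therapy a minimum of 6 weeks prior to study entry". The Recruitment paragraph repeats this: "All patients who are a minimum of 6 weeks post treatment will be provided with information about the study". There is no upper limit, time stratum or matching on time.

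**Target.** The background hypothesis is about "a subset of H&N cancer patients who experience chronic pain beyond treatment completion". In section 2.0, Aim 2 is "To correlate the presence of chronic systemic symptoms with pain phenotype". The background also cites a prevalence figure: "as many as 28% of survivors continue to have moderate pain six months after treatment completion".

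**Cohort assignment.** Under Phenotype Designation in section 3.0, three assessors sort patients into no pain, central pain or nociceptive pain. They use the Central Sensitivity Inventory, the Fibromyalgia Diagnostic Tool and the Head and Neck Pain Inventory. The protocol states no minimum symptom duration for any of these. Section 4.0 describes the pain rating on the last of them as a scale "of 1-10 in the past week, describe the type of pain they are experiencing". Each cohort is filled to 25.

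**Analysis.** Section 10.0 compares subscale scores from the VHNSS plus General Symptom Survey, the POMS and the NRS across pain groups by analysis of variance. It names no covariate and no sensitivity analysis. It describes no model for the Aim 1 MRI comparison.

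**Data.** PRO Data Collection in section 3.0 takes disease and treatment data from the medical record. The treatment completion date is not among the examples listed.

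**The concern.** The cohorts are not randomised. They are formed from symptoms reported at one point, in people who may be six weeks or many years past treatment. A variable related to both cohort label and outcome can produce or conceal a cohort difference, and time since treatment is an obvious candidate.

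The protocol supports the mechanism. Its background says that combined surgery and radiation commonly cause acute as well as chronic pain, while its figures for lasting pain are about 20%, 23% and 28%. Those figures use different definitions, but they suggest that some early pain resolves. The outcome side is also exposed: the VHNSS measures treatment-related symptoms, including mucositis, swallowing and nutrition, and section 10.0 analyses its subscales.

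For Aim 1, the background attributes conflicting MRI findings in the literature to samples that mix stages of disease. An unrecorded mix of times since treatment risks the same difficulty here.

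At stake is whether a cohort difference in symptoms or MRI can be attributed to pain phenotype rather than recency of treatment, and whether conclusions may use the word chronic.

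**Working it through.** **1. The plan's own figure.** Section 10.0 states that a difference of 0.35 on a 0-10 subscale needs about 25 per group for 80% power. It gives neither SD nor alpha, so the figure cannot be derived from the document. With three groups and alpha 0.05 assumed:
- Read as Cohen's f, 0.35 needs 28 per group; 25 per group gives 76.1% power.
- Read as a raw difference, 25 per group fits a pairwise SD of about 0.44.

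The present point does not depend on that figure. I use 0.35 only as the plan's stated scale of interest.

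**2. Possible size of the bias.** The documents give no distribution of entry times and no early-versus-late score gap, so both inputs are assumptions.

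Bias = (difference between cohorts in share of early entrants) × (mean early excess in score)

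| Imbalance | Early excess (points) | Bias (points) |
|---|---|---|
| 0.10 | 1 | 0.10 |
| 0.20 | 2 | 0.40 |
| 0.25 | 2 | 0.50 |
| 0.40 | 3 | 1.20 |

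**3. Direction.** If early entrants gather in a pain cohort, the bias adds to the contrast with the no-pain cohort. If recent local treatment pain is instead classed as nociceptive, the nociceptive cohort's scores rise and the central-versus-nociceptive contrast shrinks. With a 0.40 shift, a true central excess of 0.35 would appear as 0.35 − 0.40 = −0.05.

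**4. Effect on the test.** Suppose one of three cohorts of 25 is shifted by b through timing alone, with no phenotype effect. Then f = (b/SD) × √2/3, and the noncentral F gives the rejection rate of a nominal 5% ANOVA:

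| Shift b | SD 0.44 | SD 1 | SD 2 |
|---|---|---|---|
| 0.10 | 12% | 6% | 5% |
| 0.40 | 91% | 28% | 10% |

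The consequence ranges from negligible to severe, depending on values that the documents do not supply.

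**5. Cost of adjusting.** Take the effect that 25 per group detects with 80% power (f = 0.366). Add one covariate and divide the noncentrality by an assumed variance inflation factor (VIF) for overlap between time and cohort:
- no overlap: power 80.0%
- VIF 1.10: power 75.8%; 25 × 1.10 = 27.5, so about 28 per group to restore 80%
- VIF 1.25: power 70.0%; 25 × 1.25 = 31.25, so about 32 per group

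**The case against.** The strongest reply is that nothing in the documents shows bias. A reader might infer that resolving toxicity is in fact being analysed as chronic pain, and that the comparison is confounded. That goes too far: size and direction are both unknown. The background also says that some patients become gradually more sensitive beyond the course of treatment and that widespread pain may last indefinitely, so central pain could be commoner among later entrants. This stands, and it limits the point to what timing can do.

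A reader might also take six months as the protocol's definition of chronic. It is only the time point of one cited prevalence figure. Nor does the sentence "The exaggerated response to pain eventually returns to baseline after removal of the stimulus" show that six weeks is too early: it describes primary hyperalgesia and gives no time scale.

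Three further replies have some force:
- The cohort criteria come from cited instruments that are only summarised here and may carry their own duration element. The absence of one in the protocol is therefore weak evidence that the central cohort contains transient states.
- Hypothesis 2 names the General Symptom Survey, whereas mucositis, swallowing and nutrition are VHNSS domains. Section 10.0 nevertheless analyses both.
- This is a cross-sectional pilot, and the course over time is left to later studies. The plan still tests for significant group differences and intends the results as a foundation for that work.

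None of these replies supplies a way to detect or remove an imbalance in time since treatment if one occurs.

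**Conclusion.** The point holds as a gap in the analysis plan. Entry times may run from six weeks to any later time, the aims concern chronic states, and the one stated comparison ignores time since treatment. Confounding is possible in either direction. Under the assumed inputs its size runs from 0.10 to 1.20 points against a stated target of 0.35, and the lower end would hardly disturb the test.

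The documents do not support saying that the results will be biased, that any bias must favour a finding, or that the six-week minimum is wrong. The case for change is that a non-randomised comparison should account for an evident prognostic variable whose date is already needed to confirm eligibility. The lack of any Aim 1 model is a separate omission; this point asks only that time be included once that model is written.

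**What to change.** 1. Record the date on which treatment ended, and derive the time from it to the questionnaires and to MRI. Report the distribution by cohort.
2. In section 10.0, prespecify that time (for example, log months) as a covariate in the Aim 2 comparison and in the Aim 1 cohort comparison.
3. Prespecify a sensitivity analysis of both comparisons in later entrants, for example at least 6 months after treatment. State that this cut-off is borrowed from the cited prevalence figure and does not define chronic. Word conclusions about chronic symptoms in line with that analysis.

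The cost is one derived variable, some analysis-plan text and one degree of freedom. If time overlaps with cohort, precision is also lost: power of about 76% or 70% instead of 80% under the assumed VIFs of 1.10 and 1.25. That loss arises only when the imbalance that makes adjustment worthwhile is present. The sensitivity set will be smaller, by an amount the documents do not allow one to state. No change to eligibility is proposed.
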